1. BACKGROUND

1.1 BACKGROUND ON ACUTE ISCHEMIC STROKE

Stroke is the fourth leading cause of death and a leading cause of disability in the United States (U.S.). Nearly 800,000 strokes occur in the U.S. annually; of these, approximately 85% are ischemic in nature (Rosamond et al. 2007). Treatment options are limited, as the only approved therapy for acute ischemic stroke (AIS) is alteplase, which is to be used in eligible patients and started within 3 hours from the onset of stroke symptoms. Stroke with “only minor or rapidly improving stroke symptoms” is considered a relative exclusion by national clinical guidelines, as these patients were largely excluded from definitive trials to date (Jauch et al. 2013). Consistent with this recommendation, only 15% of alteplase recipients have mild strokes (Smith et al. 2011).

More than half of all ischemic stroke patients have mild strokes at initial presentation in population-based studies (Dhamoon et al. 2009; Reeves et al. 2013). Yet, a substantial proportion (31%–52%) of ischemic stroke patients who arrive within 2– 3 hours of symptom onset are not treated with intravenous (IV) alteplase primarily due to mild symptoms at the time of the treatment decision (Smith et al. 2011; De Los Rios la Rosa et al. 2012). In a national registry, among 93,517 cases arriving to Emergency Departments within 2 hours, 29,200 (31%) were not treated solely due to mild or improving symptoms, and 80.1% of untreated cases had a National Institutes of Health Stroke Scale (NIHSS) score ≤ 5 (Smith et al. 2011).

While treatment of mild stroke is generally uncommon, leading stroke centers vary widely in their approach. For example, the proportion of mild stroke patients (NIHSS ≤ 3) treated with reperfusion therapies at National Institutes of Health/National Institute of Neurological Disorders and Stroke (NINDS) Specialized Programs of Translational Research in Acute Stroke (SPOTRIAS) centers ranged from 2% – 16% in 2008 – 2009 (Willey et al. 2012). This variability in approach is also evident upon discussion with former leaders of the pivotal NINDS trials; some physicians treat all eligible stroke patients regardless of severity, and others treat only a minority of patients (████████ personal communication). There is unquestionable community equipoise regarding the acute treatment of the mild stroke population.

1.2 BACKGROUND ON ALTEPLASE

1.2.1 Fibrinolysis and Tissue Plasminogen Activator

Physiologic dissolution of a thrombus depends primarily on the proteolytic action of plasmin formed from plasminogen at the site of a clot. The mechanism for this activation in vivo has not been definitively established. Plasminogen, the zymogen precursor of plasmin, may be activated by substances found in the plasma milieu, in tissue (tissue plasminogen activator [t-PA]), in urine (urokinase), and in bacteria (streptokinase). The generated plasmin may be inhibited by plasma proteins such as $\alpha 2$ -antiplasmin and $\alpha 2$ -macroglobulin (Robbins 1982).

Alteplase—Genentech, Inc.
21/Protocol ML29093, Version 3

Kinetic analyses suggest that plasminogen activation in the presence of fibrin occurs after the binding of plasminogen and t-PA at the clot site. t-PA has a high affinity for fibrin, thereby efficiently activating the fibrin-bound plasminogen and converting it to plasmin. Plasmin, which when bound to fibrin is protected from rapid inactivation by α_2 -antiplasmin, then proceeds to digest the fibrin clot.

See the Activase® (alteplase) U.S. Package Insert (USPI) for additional details on nonclinical and clinical studies.

1.3 STUDY RATIONALE AND BENEFIT-RISK ASSESSMENT

Alteplase is the only approved therapeutic agent for the treatment of AIS and is widely accepted as the standard of care for eligible patients (Edlow et al. 2013; Jauch et al. 2013). The currently approved alteplase USPI contains wording that recommends against use of alteplase in patients with “minor neurological deficit or with rapidly improving stroke symptoms” due to the fact this patient population has not been evaluated. Furthermore, the current American Heart Association/American Stroke Association Council Guidelines include “minor and rapidly improving stroke symptoms (clearing spontaneously)” as a relative exclusion criterion for alteplase (Jauch et al. 2013). This is largely due to the aforementioned label wording not recommending treatment of patients with minor neurological deficit or with rapidly improving stroke symptoms (RISS), the lack of a consistent and consensus definition on who constitutes this patient population, and the absence of definitive evidence of alteplase efficacy in this setting (Levine et al. 2013). Therefore, this trial is designed to evaluate the efficacy and safety of alteplase in confirmed AIS patients with minor neurological deficit or with RISS, which will be referred to collectively as “mild stroke” throughout the protocol.

To date, all completed major randomized acute stroke trials have excluded patients with mild strokes to varying degrees. In the two NINDS trials, such patients were excluded according to the protocol (largely to prevent patients with transient ischemic attacks from being enrolled if they were having rapidly improving symptoms), but did not include an explicit definition of mild stroke except for pure sensory stroke, isolated ataxia, isolated dysarthria, and isolated facial weakness (NINDS rt-PA Study Group 1995). The operational definition for stroke symptoms too mild to treat was left to the judgment of the randomizing physician (Levine et al. 2013). Interestingly, a post hoc analysis of the 624 patients in the NINDS trial revealed that there were 58 patients (9%) enrolled with an NIHSS score ≤ 5 , none of whom had isolated motor symptoms, isolated facial droop, isolated ataxia, dysarthria, isolated sensory, and three or fewer of each of additional isolated deficits (Khatri et al. 2010). Perhaps more significantly, 2971 patients were excluded primarily due to “rapidly improving” or “minor symptoms.” However, a significant unmet medical need exists for patients with mild stroke. Available outcome data for patients with mild stroke who do not receive alteplase consistently demonstrate a high rate of suboptimal outcomes. Specifically, in two different prospective databases

Alteplase—Genentech, Inc.
22/Protocol ML29093, Version 3

of patients with mild deficits (NIHSS score ≤ 5) and no baseline disability, approximately one-third (29%–32%) were significantly disabled (as measured by modified Rankin Scale [mRS] score 2–6) at 90 days (Fischer et al. 2010; Khatri et al. 2012; [REDACTED], personal communication).

Existing, albeit limited, data suggest that the potential benefit-risk ratio for alteplase in mild stroke should be favorable. Gonzales et al. demonstrated better functional outcomes among mild strokes treated with IV alteplase compared to those not treated in a large, single-center, retrospective cohort; this was shown with two different thresholds of stroke severity (NIHSS ≤ 7 and NIHSS ≤ 3) (Gonzales et al. 2006). Additionally, a recent post hoc analysis of the subset of the third International Stroke Trial (IST-3) patients with mild strokes (pre-treatment NIHSS ≤ 5 who met all other NINDS rt-PA study eligibility criteria) showed a trend toward benefit for alteplase ([REDACTED], personal communication). For PRISMS, the primary efficacy outcome assumption (mRS 0–1) is a 9% absolute treatment effect of alteplase relative to placebo. This assumption is based on several retrospective analyses of similar patient populations (Köhrmann et al. 2009; Fischer et al. 2010; Hassan et al. 2010b; Khatri et al. 2012) as well as the aforementioned IST-3 trial subgroup analysis ([REDACTED], personal communication).

The most prevalently reported and life-threatening adverse event (AE) associated with alteplase treatment for acute ischemic stroke is symptomatic intracranial hemorrhage (sICH). Post hoc analyses, case series, and retrospective studies in patients with mild stroke suggest an absolute sICH rate of 0–2% with alteplase treatment (NINDS rt-PA Study Group 2005; Baumann 2006; Gonzales et al. 2006; Köhrmann et al. 2009; Steffenhagen et al. 2009; Hassan et al. 2010a; Hassan et al. 2010b; Huisa et al. 2012). These data are consistent with analyses of IV alteplase trials of more severe patients suggesting that stroke severity, as measured by the NIHSS score, is a strong predictor of sICH risk (Khatri et al. 2007). No data exist to estimate the sICH rate for patients with mild stroke who did not receive t-PA; therefore, for this study, we are using a 0% sICH rate for the placebo arm, which is likely a conservative estimate. An absolute sICH difference of 2% at 36 hours (primary safety endpoint) has been assumed for the alteplase arm vs. the placebo control arm in the proposed study. For this study, sICH has been defined as any neurologic decline attributed to intracranial hemorrhage (ICH) seen on imaging by the local investigator within 36 hours of study drug administration, consistent with the NINDS trial definition for sICH (NINDS rt-PA Study Group 1995).

Assuming the proposed study demonstrates both a 9% absolute treatment effect rate, the number of patients needed to treat (NNT) to show benefit (i.e., mRS score of 0–1) for one patient is 11. Assuming a 2% absolute difference in sICH rate in patients treated with alteplase, the corresponding value for the number needed to harm (NNH), specifically for sICH, is conservatively estimated to be 50. The actual number NNH, or the number of patients who would have worse outcomes at 90 days with alteplase compared to placebo treatment, is likely to be much higher than is reflected by the sICH

Alteplase—Genentech, Inc.
23/Protocol ML29093, Version 3

rate alone, as many patients who experience sICH have severe baseline infarcts and are destined for poor outcomes (Saver 2007).

For comparison, the absolute treatment effect for mRS score of 0–1 at 90 days was 13% for the NINDS-sponsored pivotal study for alteplase. This equates to an NNT of 7.9. In the same study, the absolute difference in sICH was 5.8% at 24±12 hours post-treatment, or an NNH of 17.2 (NINDS rt-PA Study Group 1995).

Table 1 Comparison of PRISMS and NINDS Studies

Study	Absolute Treatment Effect (%)	Absolute Difference in sICH (%)	NNT	NNH	LHH ^a
Proposed study in patients with mild stroke and RISS	9	2	11	50	0.22
NINDS-sponsored pivotal study for alteplase	13	5.8 ^b	7.9	17.2	0.46

LHH=likelihood of being helped vs. harmed; NINDS=National Institute of Neurological Disorders and Stroke; NNH=number needed to harm; NNT=number needed to treat; RISS=rapidly improving stroke symptoms; sICH=symptomatic intracranial hemorrhage.

^a LHH is the likelihood of being helped versus harmed and is the ratio between the NNT and the NNH. The LHH has been proposed as an expression to capture both the NNT and the NNH into a single value. An LHH below 1.0 indicates the expected benefits outweigh the possible harm. The lower the LHH, the more favorable the benefit-risk ratio is for the treatment in the patient population of interest (Demaerschalk 2007).

^b In the NINDS study, patients who received alteplase and developed sICH within 36 hours had a mortality rate of 45% (NINDS rt-PA Study Group 2005).

2. OBJECTIVES

2.1 PRIMARY OBJECTIVE

The primary objective of this study is to determine the efficacy of IV alteplase for treatment of AIS in patients with mild stroke (also known as “minor neurologic deficit” and “rapidly improving stroke symptoms”), defined as an NIHSS score ≤ 5 and not clearly disabling, within 3 hours of last known well time as measured by the proportion of patients with mRS score of 0–1 at Day 90.

2.2 SECONDARY OBJECTIVES

The secondary objectives of this study are as follows:

- To further evaluate efficacy of IV alteplase to improve mild stroke outcomes at Day 90 via:
 - Ordinal mRS
 - Global favorable recovery (Global Outcome Measure derived from mRS 0–1, NIHSS 0–1, Barthel Index [BI] ≥ 95 , and Glasgow Outcome Scale [GOS]=1)
- To evaluate safety as measured by:

Alteplase—Genentech, Inc.
24/Protocol ML29093, Version 3

- sICH within 36 hours (primary safety assessment)
- Any ICH within 36 hours
- Mortality within 90 days
- Stroke-related and neurological deaths within 90 days
- Incidence, severity, and spectrum of all AEs and serious adverse events (SAEs)

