4.6.5 Visit 5 (Day 90 [± 14 Days])/Study Completion)

Primary and secondary efficacy endpoints, as well as all exploratory endpoints, will be assessed at Day 90 with the patient. The following assessments will be performed:

- NIHSS score ([Appendix 7](#))
- Patient survival
- mRS ([Appendix 8](#))
- GOS ([Appendix 9](#))
- BI ([Appendix 10](#))
- EQ-5D ([Appendix 4](#))
- SIS-16 ([Appendix 5](#))
- CES-D ([Appendix 6](#))
- Cognitive assessments ([Appendix 11](#))
 - Controlled Oral Word Association test
 - HVLT-R trials 1, 2, and 3
 - Digit symbol coding from the WAIS III
 - Forward and Backward Digit Span test
 - Benton Judgment of Line Orientation test, form V
 - HVLT-R trial 4 and recognition
 - Animal Naming test

¹ AE/SAE collection should be started as soon as study drug administration (bolus) is initiated.

- BNT 15-item short form

The above cognitive assessments will be provided in Spanish for those patients requiring translations with the exception of the BNT 15-item short form.

- Walking speed ([Appendix 12](#))
- Concomitant medications
- SAEs and certain AEs (See Section [5.3.1](#))

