6.2 PRIMARY ANALYSIS

The primary efficacy analysis will test the hypothesis of superiority of IV alteplase therapy over standard medical care in AIS patients with mild deficits. The primary efficacy outcome is the proportion of patients with a favorable outcome, defined by mRS score of 0 or 1 at 90 days post-randomization. The difference in the proportion of mRS 0–1 responders (favorable outcome) at 90 days post-randomization between the IV alteplase arm and the standard medical care arm will be compared via a Cochran-Mantel-Haenszel test, stratified by pre-treatment NIHSS score (0–2 vs. 3–5), age (<65 vs. ≥65), and last known well time to treatment (0–2 hours vs. >2–3 hours). The primary efficacy analysis will include all randomized patients, with patients grouped according to the treatment assigned at randomization adhering to the ITT principle. As a sensitivity analysis, results from the univariate Pearson's chi-square test will also be presented.

As a supportive, secondary analysis, an ordinal (or "shift") analysis of the distribution of the mRS will be analyzed via proportional odds model if the proportionality assumption holds, and by the Mann-Whitney superiority measure if the proportionality assumption does not hold. The proportionality assumption will be assessed using the score test as well as clinical judgment on the similarities of the different odds ratios. As a secondary efficacy outcome, the global outcome score at 90 days will be analyzed using the global odds ratio test based on the generalized estimating equations analysis (Wald-type χ^2)

Alteplase—Genentech, Inc.
58/Protocol ML29093, Version 3

test) with unstructured covariance-correlation matrix. These results will be treated as supportive evidence (or lack thereof) of the treatment effect rather than conclusive evidence. The significance of each test is determined at the two-sided alpha level of 0.05. The specific statistical model for analyzing each of these outcome measures will be detailed in the Statistical Analysis Plan (SAP).

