22	
(11) Extinction and Inattention (Neglect)
 
Sufficient information to identify neglect may be obtained during the prior testing. If the patient has a severe visual loss preventing visual double simultaneous stimulation, and the cutaneous stimuli are normal, the score is normal. If the patient has aphasia but does appear to attend to both sides, the score is normal. The presence of visual spatial neglect or anosognosia may also be taken as evidence of abnormality. Since the abnormality is scored only if present, the item is never untestable. Coma Score "2".
	 0=No abnormality  1=Visual, tactile, auditory, spatial, or personal inattention or extinction to bilateral simultaneous stimulation in one of the sensory modalities  2=Profound hemi-inattention or hemi-inattention to more than one modality; does not recognize own hand or orients to only one side of space
23	Not applicable	
24	
Name of assessor:
 
The assessor must be a study team member who has completed NIHSS certification.
	

Appendix 8

Modified Rankin Scale (mRS)

1	Modified Rankin Scale:	 (0) No symptoms at all  (1) No significant disability despite symptoms; able to carry out all usual duties and activities  (2) Slight disability; unable to carry out all previous activities but able to look after own affairs without assistance  (3) Moderate disability requiring some help, but able to walk without assistance  (4) Moderately severe disability; unable to walk without assistance and unable to attend to own bodily needs without assistance  (5) Severe disability; bedridden, incontinent, and requiring constant nursing care and attention
2	For response 2 above, specify the previous activities that can no longer be carried out:	
3	Name of assessor: The assessor must be a study team member who has completed mRS certification.	

Alteplase—Genentech, Inc.
83/Protocol ML29093, Version 3

Appendix 9

Glasgow Outcome Scale (GOS)

Note: The scale presented here is based on the original article by Jennett and Bond. It has become common practice in clinical trial administration, however, to use a modified version that places the scores in reverse order (i.e., "good recovery" = 1, "moderate disability" = 2, etc.).

Score	Description
1	DEATH

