2	PERSISTENT VEGETATIVE STATE Patient exhibits no obvious cortical function.
3	SEVERE DISABILITY (Conscious but disabled). Patient depends upon others for daily support due to mental or physical disability or both.
4	MODERATE DISABILITY (Disabled but independent). Patient is independent as far as daily life is concerned. The disabilities found include varying degrees of dysphasia, hemiparesis, or ataxia, as well as intellectual and memory deficits and personality changes.
5	GOOD RECOVERY Resumption of normal activities even though there may be minor neurological or psychological deficits.

TOTAL (1-5): _____

References

Provided by the Internet Stroke Center — www.strokecenter.org

Alteplase—Genentech, Inc.
84/Protocol ML29093, Version 3

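### The global secondary endpoint counts GOS = 1 as favorable, but Appendix 9 scores 1 as death and 5 as good recovery, and the protocol never says which direction applies

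*Protocol*

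**What the plan says.** All references are to the current text, Version 3.

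- **Endpoint.** The Synopsis, Section 2.2 and Section 3.5.1 define global favorable recovery from mRS 0–1, NIHSS 0–1, Barthel Index of at least 95, and "Glasgow Outcome Scale [GOS]=1".
- **Instrument.** Section 4.6.5 lists the GOS among the Day 90 assessments and refers to Appendix 9. This is the only GOS form in the protocol.
- **Form.** Appendix 9 gives score 1 to death and score 5 to "GOOD RECOVERY Resumption of normal activities even though there may be minor neurological or psychological deficits". The rater enters a total between 1 and 5.
- **Note on the form.** It opens with "The scale presented here is based on the original article" and adds that it has become common in trials "to use a modified version that places the scores in reverse order", so that good recovery is 1 and moderate disability is 2.
- **Analysis.** Section 6.2 states that "the global outcome score at 90 days will be analyzed using the global odds ratio test based on the generalized estimating equations analysis", and that "The significance of each test is determined at the two-sided alpha level of 0.05". It treats the secondary results as supportive, not conclusive.
- **Exploratory use.** Section 3.5.3 also lists the GOS at Day 90 as an exploratory outcome, without giving its direction.

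**The concern.** The score that the endpoint calls favorable is the score that the form calls death. No sentence settles which direction the trial uses, and none says that form scores are recoded before the endpoint is derived. Two things can then go wrong.

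1. An analyst who applies the written cut-off to the written form gets a GOS component that runs backwards. Its success rate is the Day 90 death rate, and every good recovery is a failure.
2. The form collects a number, and its note describes two opposite numberings. Across about 75 sites, one rater could enter 5 and another 1 for the same good recovery. A recoding rule applied afterwards to all patients would not repair such a mixture.

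The global measure is one of only two secondary efficacy outcomes. The direction of the error also matters: with the literal coding, an excess of deaths on alteplase would add to the apparent benefit on that component. The exploratory GOS outcome inherits the same ambiguity.

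**Working it through.** **Step 1. The passages side by side**

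| Day 90 state | Score on Appendix 9 as printed | Score on the reversed scale in the note | Favorable if GOS = 1 is applied to the printed form? | Favorable if applied to the reversed scale? |
|---|---|---|---|---|
| Death | 1 | 5 | Yes | No |
| Good recovery | 5 | 1 | No | Yes |

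GOS = 1 fits an endpoint called favorable recovery only on the reversed scale, which is not the scale printed.

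**Step 2. What does not depend on the GOS**

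The sample size uses only the mRS proportions, 65% and 74%. The unpooled two-proportion formula gives, per arm,

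(0.65 × 0.35 + 0.74 × 0.26) × (1.960 + 0.842)² / 0.09² ≈ 407, or 814 in total.

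A non-binding O'Brien-Fleming-type futility look at 50% multiplies this by 1.0525, giving 856. Then 856 / 0.95² = 948. The stated figures reproduce, and no GOS input enters.

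**Step 3. The GOS component alone**

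The protocol gives no GOS or death rates for this trial, so those used here are assumptions. The odds ratio for alteplase is [pA/(1 − pA)] / [pC/(1 − pC)].

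| Coding | Control | Alteplase | Component OR |
|---|---|---|---|
| Literal (success = death) | 1% | 1% | 1.0 |
| Literal | 1% | 1.9% | 1.92 |
| Literal | 1% | 2% | 2.02 |
| Literal | 1% | 3% | 3.06 |
| Reversed (success = good recovery) | 65% | 74% | 1.53 |
| Reversed | 80% | 85% | 1.42 |

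With 474 patients per arm, 1% against 2% is about 5 against 9 deaths. On this component alone, more deaths on alteplase would read as benefit.

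**Step 4. The global odds ratio**

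This was simulated with 474 patients per arm and a GEE with unstructured working correlation and a robust Wald test. The assumptions were control favorable rates of 65%, 75%, 88% and 70% for mRS, NIHSS, BI and GOS, a latent correlation of 0.8 and a common odds ratio of 1.53. Repeated runs used 800 to 1,500 trials per scenario. The ranges below span those runs.

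| Deaths, control vs alteplase | Global OR, correct coding | Global OR, literal coding | Power, correct | Power, literal |
|---|---|---|---|---|
| 1.0% vs 1.0% | 1.53–1.54 | 1.49 | 92–93% | 89–91% |
| 1.0% vs 1.9% | 1.52–1.53 | 1.56–1.57 | 92–93.5% | 95–97% |

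In relative terms, 1.49/1.53 = 0.974 and 1.57/1.53 = 1.026, so the shift is about 3% either way.

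The shift is small because a rare component carries little information. Roughly, information is proportional to p(1 − p): 0.01 × 0.99 = 0.0099 for the miscoded component, against 0.70 × 0.30 = 0.21 when it is coded correctly.

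The 0.9-point excess is 0.02 × 0.45. The 2% is the sICH difference assumed in Section 1.3. The 45% is the mortality after sICH in a footnote to the NINDS row of Table 1. The protocol does not apply that 45% to this trial, so the scenario is an illustration and not a planning figure.

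**The case against.** A reader might infer that the plan counts deaths as successes. The documents do not support that as a statement of fact, for four reasons.

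- **Intent.** The endpoint is named favorable recovery, and the note on the form gives a numbering in which good recovery is 1. Version 1 used GOS 0–1, and Version 2 changed this to GOS = 1. That change fits a reversed scale on which 1 is the single best category.
- **Scope.** A death is not mRS 0–1 and would not be expected to meet NIHSS 0–1 or BI of at least 95. It could count as favorable on one component of four, not on the global measure as a whole.
- **Derivation rules.** The mRS form stops at 5, although Section 1.3 speaks of scores 2–6, and the Barthel form has no category for death. Survival is recorded separately. A rule for deaths is therefore needed anyway, and such rules are commonly left to the SAP. Neither the SAP nor the eCRF is shown, and the eCRF may already carry the reversed order.
- **Consequence.** The endpoint is supportive, the simulated shift is small, and a component at about 1% favorable beside others at 65–88% would be noticed.

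The first two points stand and limit the claim to an unstated direction. The third stands only in part. The protocol itself fixes both the cut-off and the form, and they conflict. An SAP can recode scores only if it knows which numbering each rater used. The fourth lowers the priority but does not remove the contradiction.

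**Conclusion.** The point holds as a contradiction between an endpoint definition and the form it relies on, with the direction of the scale left unstated. It should be fixed, but it does not threaten the trial's main conclusion.

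Harm arises only if form scores are analyzed without recoding or if sites mix the two numberings. It is then confined to the GOS component of the global measure and to the exploratory GOS outcome. The primary mRS analysis and N = 948 are unaffected.

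If the literal coding were applied to every patient, the global odds ratio would move by about 3%: from 1.53 to 1.49 with equal deaths, or to about 1.57 with a 0.9-point excess on alteplase. These figures rest on the assumed component rates, correlation and death rates in the working. Mixed numbering across sites was not simulated, so its size is not known.

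**What to change.** 1. In the Synopsis, Section 2.2 and Section 3.5.1, define the component by its label: GOS category of good recovery.
2. Bring Appendix 9 into line. Either print the reverse-ordered scale (1 = good recovery to 5 = death), or keep the printed form and state that its score 5 is the favorable category. Check that the eCRF shows the same order with labels.
3. Derive the component, and the exploratory GOS outcome, from the category label and not from the raw number.
4. Check any GOS scores already collected against recorded Day 90 survival and mRS. A score of 1 in a living patient with mRS 0–1 shows that the rater used the reversed numbering.

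The cost is a one-line change to the definition or the form and a data-management check. No patients, visits or assessments are added.
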